4.3 Schedule of Assessments

Table 2. Schedule of Assessments and Events - Randomization Phase

	SCR	Baseline	Wk 4	Wk 8	2-Wk Post Last Dose (ONLY for subjects NOT entering extension phase or who discontinue early)	Additional Instruction
Visit	Visit 1	Visit 2	Visit 3	Visit 4	Visit 5	
Eligibility Assessments						
Informed Consent	Х					
Inclusion/Exclusion	Х					Should be re-reviewed at Baseline
Medical History	Х					
Demographic Assessment	Х					
Disease History	Х					
Neurological Exam	Х			Х		
Mini Mental State Exam (MMSE)	Х					
Pregnancy Test for WOCBP (serum)	X	Х		Х		
Pregnancy Test for WOCBP (urine)	^	X	Х	^		To be done within 72 hours prior to dosing at visit 2 (Baseline Visit). The site may test a patient at any time if they suspect the patient may be pregnant.
Safety Assessments						, , , , , , ,
Laboratory Assessments including						No fasting required
urinalysis	Х	Х		Х	X	ino iasting required
Serum Chemistry			х			A physician who is not the SARA rater must b available to review lab tests and manage any potential medical evaluation throughout the randomization phase
Physical Exam						PE will be done at W4 if warranted by
	Х			Х		emergence of new AE's
Physical Measurements	Х	Х	X	X		
Vital Signs	Х	Х	Х	Х		
12-Lead ECG	Х			Х		
		X	Х	Х	X	
Concomitant Medication Review	Х	^				
	X	X	X	X	X	
Concomitant Medication Review Adverse Event Assessments Sheehan Suicidality Tracking Scale (STS)	X		X	×	X	
Concomitant Medication Review Adverse Event Assessments Sheehan Suicidality Tracking Scale		х				This should be the first clinical outcome

Visit Window is +/- 2 days during the Randomization Phase

Table 3. Schedule of Assessments and Events - Extension Phase

	¹ Baseline Visit	Ext. Wk 4	Ext. Wk 8	Ext. Wk 12	Ext. Wk 24	Ext. Wk 36	Ext. Wk 48
Visit		Visit 1	Visit 2	Visit 3	Visit 4	Visit 5	Visit 6
Eligibility Assessments							
⁴ Informed Consent	Х						
Neurological Exam					Х		Х
Pregnancy Test for WOCBP (serum)	Х				Х		Х
² Pregnancy Test for WOCBP (urine)	Х	Х	Х	Х		Х	
Safety Assessments							
Laboratory Assessments including urinalysis	х				Х		Х
³ Lab: LFT tests only (ALT, AST, BILI, GGT)		х	Х	Х		Х	
Physical Exam	Х				Х		Х
Physical Measurements	V	V	V	V	V	V	V
Vital Signs	X	X	X	X	X	X	X
12-Lead ECG	X	^	^	^	X	^	X
Concomitant Medication Review	X	X	Х	X	X	X	X
Adverse Event Assessments	х	х	х	х	х	х	Х
Sheehan Suicidality Tracking Scale (Sheehan STS)	X	X	Х	Х	Х	Х	Х
* Clinical Outcome Assessment							
SARA	х		X		х	Х	Х
Clinical Drug Supply							

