6.2 Safety Assessments

Safety and tolerability will be evaluated by report of adverse events (AE) and by evaluation of abnormalities and clinically significant changes in physical examinations, ECGs, vital signs, and laboratory tests.

The SARA rating (primary outcome measure) must NOT be performed by the staff (including principal investigator) who are evaluating test lab results during the 8 week randomization phase. Specifically, these tests include Serum Chemistry, Hematology and Urinalysis acquired after baseline (i.e., Week 4 scheduled labs, potentially other unscheduled tests, through Week 8 scheduled labs). After completion of the Week 8 visit assessments and sign-off on SARA ratings as final, a SARA rater who is the principal investigator may evaluate labs that will be acquired within the Extension Phase. Based on this requirement, a site may potentially need to identify a qualified physician or other medical personnel who can be available to review lab tests during the randomization phase for each subject. This is further described in Section 6.3.1.

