6.2.4.5 Evaluation of Laboratory Assessments

As described above, the SARA rating (primary outcome measure) must NOT be performed by the staff (including principal investigator) who are evaluating test lab results during the 8 week randomization phase. Specifically, these tests include Serum Chemistry, Hematology and Urinalysis acquired after baseline (i.e., Week 4, potentially other unscheduled tests, through Week 8 scheduled labs). After completion of the Week 8 visit assessments and sign-off on SARA ratings as final, a SARA rater who is the principal investigator may evaluate lab tests acquired in the Extension Phase. Based on this requirement, a site may potentially need to identify a qualified Lab Monitor (i.e., physician or other medical personnel) who can be available to review labs during the randomization phase for each subject. This requirement does not apply during the Extension Phase.

The rationale for this process is to assure adequate blinding while maintaining subject safety. Riluzole itself is associated with low rates of transient increases in transaminases. According to the US Prescribing information for riluzole (the active metabolite of troriluzole), the rates of markedly elevated transaminases (AST or ALT > 5x ULN) are approximately 2%. The rates of less elevated transaminases (i.e., AST or ALT > 3x ULN) are approximately 8%. While troriluzole was designed to diminish risk for LFT changes (e.g., diminished first-pass liver metabolism, approximately 30% lower molar burden than the 100 mg dose of riluzole), the study is designed to address the possibility of such increases while maintaining the integrity of the primary outcome measure. Other lab abnormalities, based on known literature of riluzole, could include decreased neutrophil count. The Lab Monitor should manage any non-LFT lab Approved Version 08: 17 April 2020

abnormalities as medically warranted to assure subject safety. The SARA Rater (who may be the PI) should be shielded from the nature of any additional evaluation triggered by these lab tests.

The management of abnormal LFTs are described herein. Scheduled LFTs (ALT, AST, bilirubin, alkaline phosphatase) at the Week 4 and Week 8 visits will be evaluated by the Lab Monitor (LM), who will be a physician or other qualified medical personnel designated by the PI and who has no involvement in the conduct of the SARA Ratings.

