If AST or ALT values are between 3x ULN and <5x ULN, then the Lab Monitor, potentially with administrative assistance from the Study Coordinator, will medically evaluate the subject. Medical assessment of the subject can include the following:

- Must include repeat LFT assessments (ALT, AST, total and direct bilirubin, alkaline phosphatase, PT, aPTT, INR) within 1 week and follow until resolution. The frequency of the repeat tests will be clinically based on trajectory of change (e.g., improving, stable vs increasing). These tests can be performed either at a local, or preferably, central lab
- Assessment of AEs, usage of concomitant medications, exposure to potential hepatic toxins, risk factors for hepatitis or alcoholic liver disease
- Based on overall clinical presentation (severity and extent of lab abnormalities; rate of change of lab values), additional evaluations (as outlined under the scenario of ALT/AST > 5xULN) may be considered.

If the Week 4 visit shows ALT or AST>5x ULN, the Lab Monitor will notify the PI and the PI will assess this as a potential SAE. The subject will be managed as appropriate, including:

- Study medication must be discontinued immediately
- Bring subject in for physical exam and evaluation.
 - Assess for right heart failure, hypotension, and signs/symptoms of alcohol abuse
 - o assess for exposure to toxic dietary/herbal supplements and/or prescriptions drugs that are associated with hepatic effects, such as acetaminophen;
 - o assess for potential exposure to environmental toxins
 - o Evaluate for abdominal pain, splenomegaly, hepatomegaly
- Repeat LFTs (AST, ALT, total and direct bilirubin, alkaline phosphatase) as soon as possible, with either a local lab or preferably central lab; and, follow to resolution;
- Order other labs tests to rule-out other causes of lab abnormalities and to assess extent of hepatic effects
 - o coagulation factors (PT, aPTT, INR)
 - o Hepatitis A, B and C serologies
 - o Ebstein-Barr virus serology
- Assess AEs
- Consider gall bladder or ductal imaging studies if presentation suggests potential for gall stones.

Entry into the Extension Phase requires continued impression that open-label treatment offers an acceptable risk-benefit profile. If lab abnormalities in the Randomization Phase are potentially clinically significant then treatment with study drug in the Extension Phase should

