6.3.1 The Scale for the Assessment and Rating of Ataxia (SARA)

The SARA was developed as a clinician-administered instrument to measure severity of symptoms in patients with SCA. While there are multiple scales available, the SARA has been tested in the most patients with SCA to date. It has been demonstrated to have excellent interrater reliability [i.e., intraclass correlations of > 0.95 (61, 62)], good test- retest reliability [intraclass coefficient of 0.90 (61)], high internal consistency [Cronbach's alpha of > 0.94 (61, 62)], sensitivity to change over time in populations with SCA (2, 63, 64) and able to detect treatment effects (65). In addition, the SARA scores were highly correlated with measures of activities of daily living, such as the Barthel Index (typically used in stroke) and the Unified Huntingtons Disease Rating Scale Part IV (typically used in Huntingtons Disease).

The SARA scores range from 0 (no ataxia) to 40 (severe). The SARA takes approximately 15 minutes to administer. Assessed items include:

[figure not shown]
- 1. Gait (rated 0 to 8)
- 2. Stance (0 to 6)
- 3. Sitting (0 to 4)

- 4. Speech disturbance (0 to 6)
- 5. Finger chase (0 to 4)
- 6. Nose-finger test (0 to 4)
- 7. Fast alternating hand movements (0 to 4)
- 8. Heel-shin slide (0 to 4)

[figure not shown]
Once each of the 8 categories has been assessed, the total score is calculated to determine the severity of ataxia. For motor activities of the four extremities (items 5-8), assessments are performed bilaterally and the mean values are used to obtain the total score.

[figure not shown]
Raters must be pre-approved by sponsor or sponsor representative (i.e. CRO) to rate

subjects on the SARA

All subjects who discontinue study treatment early should complete an Early Discontinuation Visit as well as the 2-Week Post Dose Visit. The 2-Week Post Dose Visit would not need to occur if the subject stopped taking study medication more than 2 weeks prior to the Early Discontinuation Visit. The only exception to this requirement is when a subject withdraws consent for all study procedures or loses the ability to consent freely (i.e. is imprisoned or involuntarily incarcerated for the treatment of either a psychiatric or physical illness).

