4 ANALYSIS SETS

BHV4157 cohort: Subjects that took at least one dose of BHV4157 and provided at least one post-baseline total SARA score.

- The analysis of the FAS cohort will take into account both the dosing break between phases (Randomization and Extension) and the dosing break prior to the Expanded Extension.
- The analysis of the ITT cohort will take into account the dosing break between phases (Randomization and Extension) but not the dosing break prior to the Expanded Extension.

On-treatment data for efficacy analyses are considered as any visit that occurs within 7 days (inclusive) of the post-final study treatment dose. The Final Study Visit is considered as any visit that occurs between 8 and 21 days post-final study treatment dose.

On-treatment data for safety analyses are considered as any visit or AE recorded within 30 days (inclusive) post-final study treatment dose.

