9 AD HOC ANALYSES

Additional analyses of interest not specified directly in the SAP were analyzed using the FAS. These analyses were performed on the following data cuts:

• Randomization Phase: locked data through Extension Phase Week 48

Randomization Phase

DocuSign Envelope ID: BD8AB61B-7989-408F-A5B1-B84E58727CD3

Biohaven Pharmaceuticals Protocol BHV4157-201 SAP ver 04.0 Addendum 27Mar2020

Extension Phase – Week 48

CONFIDENTIAL

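### If a Week 4 ALT or AST above 5x ULN goes to a PI who is also that subject's SARA rater, does the protocol leave the primary endpoint unprotected?

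*Protocol*

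**What the plan says.** Protocol 6.2 sets the general rule. SARA rating "must NOT be performed by the staff (including principal investigator) who are evaluating test lab results during the 8 week randomization phase". The section counts the Week 4 labs, any unscheduled labs and the Week 8 labs among these results. Section 6.2.4.5 repeats the rule and adds the only relaxation: once the Week 8 SARA is signed off, "a SARA rater who is the principal investigator may evaluate lab tests acquired in the Extension Phase".

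The same section gives the Week 4 and Week 8 liver tests to a Lab Monitor "who has no involvement in the conduct of the SARA Ratings". Table 2 (Protocol 4.3) requires that a physician other than the SARA rater be available to review labs throughout the randomization phase.

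For a Week 4 ALT or AST above 5x ULN, 6.2.4.5 then says "the Lab Monitor will notify the PI and the PI will assess this as a potential SAE", and study drug is stopped. On who may rate, the visible part of 6.3.1 says only "Raters must be pre-approved by sponsor or sponsor representative (i.e. CRO) to rate" subjects on the SARA. Section 6.2 refers the reader to 6.3.1 for more on the separation of roles.

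**The concern.** Protocol 6.2.4.5 recognises that the PI may be the SARA rater. It keeps lab results away from raters because a raised transaminase hints at active drug. Yet the most telling liver result is sent to the PI, with no exception for a PI who rates that subject. For values from 3x to below 5x ULN, the Lab Monitor handles the matter and the text calls for no notice to the PI.

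A PI who carried out the SAE assessment and then rated the same subject would break the plan's own separation rule on its only primary endpoint. A site whose sole approved rater is the PI would also have to find a replacement during the trial. At stake is the blindness of a clinician-rated score.

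**Working it through.** **1. Do the instructions contradict each other?**

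| Provision | What it requires |
|---|---|
| Protocol 6.2 and 6.2.4.5, general rule | Whoever evaluates post-baseline labs in the 8-week phase, PI included, does not rate SARA |
| Protocol 6.2.4.5, above 5x ULN at Week 4 | The PI is told and judges whether it is an SAE |
| Protocol 6.3.1 | Only approved raters may rate |

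Judging a lab value as a potential SAE is evaluating a lab result. The second row therefore triggers the first: that PI may not rate the subject again before Week 8 sign-off. The third row says who may take over, namely another approved rater. All three can be followed together. Only the sentence that spells out the handover is missing.

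Sending the result to the PI also has a reason. Protocol 8.1.3 makes the investigator responsible for reporting SAEs, within 24 hours.

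**2. The plan's own figure.** Inputs from Protocol 9.2 and SAP 4.1: difference 1.24, SD 2.01, 56 per group, two-sided alpha 0.05.

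- SE = 2.01 × √(2/56) = 0.380.
- Two-sample t-test power = 0.899, which agrees with the stated value of about 90%.

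**3. How many subjects?** Inputs: about 120 randomized 1:1, so 60 on active drug; riluzole rate of about 2% for values above 5x ULN (Protocol 6.2.4.5), assumed to apply to troriluzole.

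- Upper bound, with every event at Week 4 and every subject PI-rated: 60 × 0.02 = 1.2 expected; 1 − 0.98^60 = 70% chance of at least one.
- Half of events at Week 4 and half of subjects PI-rated (both assumptions): 60 × 0.02 × 0.5 × 0.5 = 0.3; 1 − 0.995^60 = 26%.
- As above with a 1% rate (assumption): 60 × 0.01 × 0.25 = 0.15; 1 − 0.9975^60 = 14%.

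**4. Effect on the test.** Assume that every such rating is off by 1 to 2 points and enters the Week 8 comparison. Mean shift = proportion affected × error. Type I error comes from the noncentral t distribution with 110 df and SE 0.380.

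| Case | Shift in arm mean | Two-sided type I error |
|---|---|---|
| Upper bound (2% of the arm) | 0.02 to 0.04 | 5.03% to 5.12% |
| Reduced case (0.5% of the arm) | 0.005 to 0.01 | 5.00% to 5.01% |

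The assumed treatment difference is 1.24.

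**5. Would such a rating reach Week 8?** Protocol 6.3 puts SARA before the other assessments, so the Week 4 score normally precedes the lab result. Only later scores are exposed.

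- Week 4 visit: 28 ± 2 = Days 26 to 30.
- Last dose 1 to 5 days later (assumption): Days 27 to 35.
- Post-dose visit, 14 ± 2 days after the last dose: Days 39 to 51.
- Week 8 analysis window (SAP 4.2.9, ±1 week): 56 ± 7 = Days 49 to 63.

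The ranges overlap on Days 49 to 51, so timing alone does not keep such a visit out. Section 4 of the SAP addendum states: "On-treatment data for efficacy analyses are considered as any visit that occurs within 7 days (inclusive) of the post-final study treatment dose". If that rule covers this phase, which the addendum does not make clear, the last countable score falls on Days 34 to 42 and none reaches Week 8. The SARA row of Table 2 is not legible in the public text, so it cannot be confirmed that SARA is rated at these later visits.

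**6. What if an informed PI rates anyway?** Protocol 5.5 has significant departures from study procedures documented as deviations. SAP 3.2 classes them as major, lists improper breaking of the blind among its examples, and puts all deviations in the listings. The per-protocol set (SAP 3.1) drops subjects with major deviations. Efficacy is analysed on both sets (SAP 4.6), with the per-protocol analysis as a sensitivity analysis (SAP 4.2.5).

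**The case for a change.** The best case for a change is that a safeguard should be most explicit where the signal is strongest, and here it is silent. The handover is not automatic, because a replacement must be an approved rater and a single-rater site may not have one. One sentence would settle it, and a non-rating physician is already required.

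Part of this stands. The sentence is absent from 6.2.4.5, and a reader has to combine two rules to reach the answer. But that answer is the only one consistent with the prohibition. Section 6.3.1 may state it, since its public text has gaps close to the rater requirement. Moving the SAE assessment to another physician would not be mere clarification: it would reassign a safety responsibility that the protocol gives to the PI.

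A new flag and sensitivity analysis would largely repeat the deviation and per-protocol rules. That holds only if the breach is classed as significant, which is a judgement, because a lab result is a clue to treatment and not the treatment code. New wording would probably also come too late: section 9 of the addendum already lists, as a data cut, "Randomization Phase: locked data through Extension Phase Week 48".

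**Conclusion.** No change follows. The text leaves a consequence unstated, but its own prohibition supplies it: a PI who has assessed the Week 4 result does not rate that subject again before Week 8 sign-off, and another approved rater does. Staff who follow the plan as written reach a sound result.

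Even if the rule were broken, two-sided type I error would be 5.00% to 5.01% in the reduced case and 5.12% at the top of the upper bound. These figures assume that the 2% riluzole rate carries over, that each affected score is off by 1 to 2 points, and that it counts at Week 8. The reduced case also assumes that half of events show at Week 4 and that the PI rates half of the subjects.

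Two things cannot be settled from the public text: what the incomplete parts of 6.3.1 say, and whether any SARA is rated after drug is stopped. Neither could turn so small an effect into a reason to amend the plan.

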6.2.5 Sheehan Suicidality Tracking Scale (Sheehan STS)

The Sheehan STS is a prospective, patient self-reported or clinician administered rating scale that contains 16 questions to track both treatment-emergent suicidal ideation and behaviors. Subjects who have a S-STS score > 0 should be evaluated by the investigator. If the investigator determines that a subject is at risk of suicide or self-harm, appropriate measures to ensure the subject's safety and obtain mental health evaluation must be implemented. The event should be recorded as either an AE or SAE as determined by the investigator and reported within 24 hours to the Sponsor.

6.3 Clinical Outcome Assessments

The clinical outcome assessments and other interviews/scales (e.g., Sheehan STS) should be performed at a similar time of day at each visit.

- If subjects are traveling a significant distance consideration should be given to minimizing the effects of travel fatigue.
- The order of the tests should include the administration of the SARA prior to other clinical / safety outcome assessments

6.3.1 The Scale for the Assessment and Rating of Ataxia (SARA)

The SARA was developed as a clinician-administered instrument to measure severity of symptoms in patients with SCA. While there are multiple scales available, the SARA has been tested in the most patients with SCA to date. It has been demonstrated to have excellent interrater reliability [i.e., intraclass correlations of > 0.95 (61, 62)], good test- retest reliability [intraclass coefficient of 0.90 (61)], high internal consistency [Cronbach's alpha of > 0.94 (61, 62)], sensitivity to change over time in populations with SCA (2, 63, 64) and able to detect treatment effects (65). In addition, the SARA scores were highly correlated with measures of activities of daily living, such as the Barthel Index (typically used in stroke) and the Unified Huntingtons Disease Rating Scale Part IV (typically used in Huntingtons Disease).

The SARA scores range from 0 (no ataxia) to 40 (severe). The SARA takes approximately 15 minutes to administer. Assessed items include:

[figure not shown]
- 1. Gait (rated 0 to 8)
- 2. Stance (0 to 6)
- 3. Sitting (0 to 4)

- 4. Speech disturbance (0 to 6)
- 5. Finger chase (0 to 4)
- 6. Nose-finger test (0 to 4)
- 7. Fast alternating hand movements (0 to 4)
- 8. Heel-shin slide (0 to 4)

[figure not shown]
Once each of the 8 categories has been assessed, the total score is calculated to determine the severity of ataxia. For motor activities of the four extremities (items 5-8), assessments are performed bilaterally and the mean values are used to obtain the total score.

[figure not shown]
Raters must be pre-approved by sponsor or sponsor representative (i.e. CRO) to rate

subjects on the SARA

All subjects who discontinue study treatment early should complete an Early Discontinuation Visit as well as the 2-Week Post Dose Visit. The 2-Week Post Dose Visit would not need to occur if the subject stopped taking study medication more than 2 weeks prior to the Early Discontinuation Visit. The only exception to this requirement is when a subject withdraws consent for all study procedures or loses the ability to consent freely (i.e. is imprisoned or involuntarily incarcerated for the treatment of either a psychiatric or physical illness).

7 STUDY DRUG MANAGEMENT

7.1 Description of Study Drug

7.1.1 Investigational Product

An investigational product, also known as investigational medicinal product in some regions, is defined as followed:

A pharmaceutical form of an active substance or placebo being tested or used as a reference in a clinical study, including products already with a marketing authorization but used or assembled (formulated or packaged) in a way different from the authorized form, or used for an unauthorized indication, or when used to gain further information about the authorized form

The investigational product should be stored in a secure area according to the local regulations. It is the responsibility of the investigator to ensure that the investigational product is only dispensed to study patients. The investigational product must be dispensed only from official study sites by authorized personnel according to local regulations.

In this protocol, the investigational products are: Troriluzole capsules 140 mg (and matching placebo). Troriluzole will be provided as a loose filled capsule in the Randomization Phase and as loose filled or formulated capsules (dependent on lot) in the Extension Phase. Formulated capsules have black markings on the capsule which differentiates them from the loose filled capsules. Study BHV4157-102 demonstrated bioequivalence of the two formulations.

